## STUDY DESIGN

---

### I. *Target Population and Inclusion/Exclusion Criteria*

Participants for the proposed research include up to 350 individuals ages 18 and over who will be recruited from the Albuquerque Metropolitan Area using the following inclusion criteria:

- 1) interested in reducing alcohol drinking and consumed alcohol in past 30 days
- 2) right-handed
- 3) able to communicate in English

The inclusion criteria are based on our long-term goal of developing an intervention with broad appeal for most individuals who are interested in reducing drinking. The right-handed inclusion is based on the fact that the majority of people are right-handed and the effects of tDCS may be influenced by handedness (a proxy for hemispheric dominance; Schade et al., 2012). Ultimately we plan to develop separate tDCS montages that are specific to right and left hemisphere dominance, but for the purposes of this initial study we opted for increasing internal validity by excluding left-handed individuals.

The following exclusion criteria will be used for all participants

- (1) lifetime diagnosis of schizophrenia or bipolar disorder or current SUD other than nicotine or marijuana assessed via the phone screening questionnaire
- (2) cardiac pacemaker
- (3) implantable defibrillator
- (4) metal objects in upper body that might interfere with tDCS, or that tDCS may interfere with their function, including metal plates, screws and prosthetics in head, certain older tattoos and permanent makeup using metal containing inks, aneurysm clips, neural stimulators of any kind, ear implants or hearing aids, insulin pumps, drug infusion devices and dental appliances
- (5) for females, pregnant or attempting to get pregnant
- (6) history of seizures or seizure disorder
- (7) allergic to latex, rubber, conductive medium like saline or electrode gel
- (8) if assigned to active tDCS and unable to tolerate 1.5 mA of tDCS during a baseline stimulation session
- (9) history of severe alcohol withdrawal including tremors, seizures, or delirium tremens
- (10) currently or previously prescribed anti-seizure medications or medications for alcohol withdrawal
- (11) score of 8 or greater on the Clinical Institute Withdrawal of Alcohol Assessment Scale – Revised at any tDCS sessions
- (12) unable to attend treatment groups at scheduled time and unwilling to wait for group treatment at a time that works for the participant
- (13) Arrested, charged, or convicted of a violent crime (e.g., aggravated assault) in the past 2 years or any history of assault with a deadly weapon, as indicated by the caselookup.nmcourts.cov database.

The exclusion of lifetime schizophrenia or bipolar disorder diagnoses was largely based on concerns of individuals with these disorders possibly needing a higher level of care than what we can provide as part of this study, particularly if symptoms were to be exacerbated by participation in the study. In addition, there is some anecdotal evidence that mindfulness practice may, in very rare cases, be associated with psychotic and manic episodes. To our knowledge this concern has not been verified in the empirical literature, but given the experimental and preliminary nature of the proposed study we have opted to exclude these individuals. The exclusion of individuals with comorbid drug use disorder, other than nicotine and marijuana, was desired because of the early stages of this research and the limitations of intervention content, measurement tools and cue presentation if individuals are more triggered or impacted by other drugs of abuse. Other drug use disorder could reduce applicability of an alcohol focused treatment and potentially reduce the impact of alcohol cues in the cue reactivity task. The remaining exclusion criteria, (2 to 10), were selected for safety concerns in the use of tDCS and/or EEG. The exclusion of individuals who have been arrested, charged, or convicted of a violent crime in the past 2 years or crime involving a firearm or other deadly weapon at any time is to protect the research staff and other participants from the potential of violence by a participant in the group.

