## V. *Data Collection Procedures*

**Procedures.** Following phone screen, eligible participants will be invited to the Psychology Clinical Neuroscience Center (PCNC) for the baseline session, which includes being breathalyzed to ensure a breath alcohol concentration (BAC) of 0.0, pregnancy testing for fertile female participants, providing informed consent, completing a battery of self-report and behavioral measures, baseline EEG, and baseline stimulation session. Participants who have a BAC > 0.0 will be rescheduled, given snacks and water until their BAC is reduced to < 0.04 in accordance with NIAAA guidelines, and will be provided a taxi voucher. Participants will take part in the intervention for 8 two and a half hour sessions up to 8 weeks. At each 150-minute session, participants will undergo 30 minutes of initial assessment and verification of session eligibility (e.g., breathalyzer, withdrawal assessment, pregnancy tests, and self-report), 30 minutes of tDCS during a guided meditation practice followed by 90 minutes of MBRP session content. The overarching goal of the meditation is to help participants obtain greater mental clarity through training attention and awareness, decreasing emotional reactivity, and improving general well-being. All study participants will be assigned to the MBRP condition. All tDCS sessions will be double blinded with active and sham tDCS participants within all groups. Pilot testing of this protocol has demonstrated feasibility of combining active and sham tDCS within a single group, while maintaining the blind.

**Measures.** Table 1 provides the assessment schedule for the proposed study. Consistent with the Secondary Aim to understand the mechanisms of behavior change at multiple levels of analysis, we have included self-report and behavioral assessments of inhibitory control (NIH Cognition Toolbox, UPPS Impulsive Behavior Scale, Stop Signal Task), cue reactivity and craving (Penn Alcohol Craving Scale, Cue Reactivity), and negative affect (NIH Emotions Toolbox, Negative Affect Reactivity). We have also included a blinding questionnaire to assess the degree to which individuals were blinded to the active versus sham tDCS randomization condition. Breathalyzer tests will be conducted prior to all interviews. Participants who have a BAC > 0.0 will be rescheduled, given snacks and water until their BAC is reduced to < 0.04 in accordance with NIAAA guidelines, and will be provided a taxi voucher.

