Clinical Institute Withdrawal Assessment of Alcohol Scale, Revised	Measure of current alcohol withdrawal symptoms	X		
Blinding Questionnaire	One question assessing knowledge of condition		X	

**Primary Drinking Outcome.** The *Form 90* (Miller, 1996) is a semi-structured interview that gathers daily calendar-based alcohol and illicit drug use data. A 2-month assessment window will be used at each of the time-points. The *Form 90* will be used to derive estimates of the primary outcome: drinks per drinking day. The *Form 90* has demonstrated reliability in the collection of alcohol and drug use data (Maisto, Conigliaro, Gordon, McGinnis, & Justice, 2008; Sobell, Brown, Leo, & Sobell, 1996).

**Weekly During Treatment Measures.** An abbreviated assessment battery will be administered weekly during treatment to assess state mindfulness (Toronto Mindfulness Scale (Lau et al., 2006)), mindfulness practice in the prior week, craving (PACS; Flannery Volpicelli, & Pettinati, 1999), negative urgency and lack of planning items from the UPPS (Littlefield et al., 2015; Whiteside & Lynam, 2001), and negative affect (Short Forms of Anger, Sadness, Stress from NIH Emotions Toolbox; Salsman et al., 2013).

**Behavioral Tasks.** All behavioral tasks will be completed via computer during EEG to provide a measure of electrical brain activity during rest and completion of the tasks. To examine inhibitory control, we will use a *Stop Signal Task* (Logan, Van Zandt, Verbruggen, & Wagenmakers, 2014) in which participants make left-right judgments of the directionality of an arrow presented on the screen. For each trial, a circle will appear for 500 ms, followed by a left or right-pointing arrow for up to 1 second, and between 500 ms and 2500 ms jittered inter-trial interval to reduce anticipatory responses. Approximately 25% of trials will be "stop trials" with a tone played to signal participants to inhibit the

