## **Procedures & Interventions**

**Screening (30 minutes).** Initial eligibility will be determined via telephone with a Screening Questionnaire. Individuals who do not meet criteria for the study will be referred to community drinking reduction programs. The phone screening form will be destroyed for those who are not eligible. First and last names of those who are excluded will be maintained to prevent re-screening. De-identified demographic information and reasons for ineligibility for those who are ineligible will be recorded in a separate document without identifiers for reporting purposes. Eligible individuals will be scheduled for a baseline assessment session. Phone screening forms and contact information for participants who are screened in will be maintained in a password protected file. The phone screening form will be de-identified and only linked to the participant with the participant ID.

**Baseline (up to 5 hours).** Informed consent will be obtained, and participants will complete the Handedness Questionnaire and pregnancy test (fertile female participants only). Participants will complete assessments listed in Table 1. Participants will also complete a baseline tDCS stimulation session lasting less than 10 minutes. This baseline session will be to familiarize the participants to tDCS outside of the group setting, to explain the stimulation protocol, and to answer any questions that participants might have about the tDCS procedure. Participants in the active condition who have difficulty tolerating the 2.0 mA current during the baseline stimulation session will be tested at 1.5 mA. If 1.5 mA is tolerated then participants will be enrolled in the trial at 1.5 mA. If 1.5 mA is not tolerated during the baseline stimulation session then participants will be deemed ineligible. Participants who fail study eligibility requirements at this point will be compensated for their time and referred to community alcohol treatment programs.

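### Intolerance of 1.5 mA removes people after assignment and only from the active arm, with no outcome follow-up; the bias is probably small and cheap to avoid

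*Combined protocol and SAP*

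**What the plan says.** In the Combined protocol and SAP, Study Design I (Target Population and Inclusion/Exclusion Criteria), exclusion (8) applies "if assigned to active tDCS and unable to tolerate 1.5 mA of tDCS during a baseline stimulation session".

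The Baseline paragraph of Procedures & Interventions gives the mechanics. "Participants in the active condition who have difficulty tolerating the 2.0 mA current during the baseline stimulation session will be tested at 1.5 mA". Two outcomes follow: "If 1.5 mA is tolerated then participants will be enrolled in the trial at 1.5 mA", and "If 1.5 mA is not tolerated during the baseline stimulation session then participants will be deemed ineligible". Then: "Participants who fail study eligibility requirements at this point will be compensated for their time and referred to community alcohol treatment programs".

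The baseline visit is described as "completing a battery of self-report and behavioral measures, baseline EEG, and baseline stimulation session", with the stimulation session last in the list. Form 90, the source of the primary outcome, is scheduled at baseline, post-treatment and 2 months: "A 2-month assessment window will be used at each of the time-points". The paragraphs on the post-treatment and follow-up assessments time both visits from completion of the treatment sessions.

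Study Data II (Data Analysis/Statistical Considerations) specifies maximum likelihood on the available data, a generalized linear mixed model, covariates and a check for differential attrition. It does not name the set of participants analysed. Study Data I adds monitoring of baseline equivalence.

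**The concern.** A tolerance test is neutral between arms if everyone takes it, or if it is applied without regard to allocation. This one is applied by arm. The exact moment of randomisation is not stated, but both texts make the step conditional on being in the active condition, so assignment must come first. During treatment, sham participants receive a 30-second ramp-up and then 0.0 mA, and nothing removes them for failing to tolerate 1.5 mA.

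If people who cannot tolerate the current differ in their drinking, the active arm loses them and the sham arm keeps their counterparts. That difference enters the primary contrast whether or not stimulation works. The planned analysis cannot repair it, because those removed are classed as ineligible and have no described post-baseline data. The attrition check and the equivalence monitoring do not say whether tolerance failures count.

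**Working it through.** **Inputs from the documents.** Target of 86 participants, 15% attrition, two-sided alpha 0.05, and pilot effect d = 0.43 at 2 months (Study Data II). The target follows from the 74 needed for mediation: 74 × 1.15 = 85.1, rounded up to 86 (dividing by 0.85 gives 87.1, so 88). The argument does not depend on this figure; it only sets the scale. Completers: 86 × 0.85 = 73.

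**Assumptions.** Allocation is 1:1, so 43 are assigned to active. The share failing, q, is 2%, 5% or 10%, which is 43q = 0.9, 2.2 or 4.3 people. Failures differ from the rest by D = 0.5 SD. The correlation between baseline and follow-up drinking is 0.6 where baseline is adjusted for. The tDCS Protections text (mostly mild, transient tingling) and the step-down to 1.5 mA suggest that failure is uncommon.

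**Bias with no true effect.**
- No baseline adjustment: q × D.
- Baseline drinking in the model and a difference stable over time: q × D × (1 − 0.6).
- Failures differ only in later outcome: q × D, and adjustment does not help.

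Type I error is from the noncentral t with 71 df. The noncentrality is bias × √73 / 2, divided by √(1 − 0.6²) = 0.8 when baseline is in the model.

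| q | Bias, unadjusted (share of 0.43) | Type I | Bias, adjusted, stable | Type I | Type I, adjusted, outcome-only |
|---|---|---|---|---|---|
| 2% | 0.010 (2.3%) | 0.0502 | 0.004 | 0.0501 | 0.0503 |
| 5% | 0.025 (5.8%) | 0.0513 | 0.010 | 0.0503 | 0.0520 |
| 10% | 0.050 (11.6%) | 0.0551 | 0.020 | 0.0513 | 0.0580 |

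Bias scales with D. At q = 10%, D = 0.25 gives 0.025 SD and D = 1.0 gives 0.10 SD. For the latter the unadjusted noncentrality is 0.10 × √73 / 2 = 0.427 and the type I error about 0.071. In the outcome-only case the noncentrality is 0.427 / 0.8 = 0.534 and the type I error about 0.082.

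**Could baseline data settle it?** Baseline Form 90 probably exists for failures, so they can be compared with the other active participants. With k failures the standard error is √(1/k + 1/(43 − k)), which is 1.01, 0.72 or 0.53 SD for k = 1, 2 or 4. The 95% half-widths are 2.0, 1.5 and 1.1 SD, and power to detect 0.5 SD is 8%, 10% and 15%. The comparison is possible but cannot exclude a relevant difference, and it says nothing about outcomes.

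**Cost of keeping failures in, if assignment does nothing for them.** The effect becomes 0.43 × (1 − q) = 0.42, 0.41 or 0.39. A nominal power of 0.80 becomes Φ(2.802 × (1 − q) − 1.960) = 0.78, 0.76 or 0.71. Holding 0.80 takes 86 / (1 − q)² = 90, 96 or 107 participants.

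**The case against.** The sponsor can say that this is a safety-based eligibility step taken before enrolment; the text after the exclusion list gives safety as the reason for criteria 2 to 10. That justifies stopping the current. It does not justify losing an interview outcome, and calling the step eligibility does not make it independent of arm.

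The stronger objections concern size and side effects, and much of them stands.
- Nothing in the documents links current tolerance to drinking. The power statement's three time-points and the hypothesis of larger reductions suggest that baseline drinking will be modelled, although its role is not stated. The smaller figures then apply, unless failures differ only in later outcome.
- Dilution costs 2 to 9 points of power, set against at most 0.8 points of type I error at D = 0.5.
- Retained failures who know they get no stimulation may lose an expectancy benefit that sham participants keep. An assumed loss of 0.1-0.3 SD at 10% failing is 0.01-0.03 SD, of the same order as the bias removed.
- Groups mix active and sham participants, so someone visibly without a device could reveal their arm. The fix has to deal with this.

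A reader might infer that the rule inflates the apparent benefit of active tDCS, or that it invalidates the trial. The documents support neither: they give no failure rate and no sign for the difference. Nor should much be made of the lead-in, "The following exclusion criteria will be used for all participants". Criterion (5) in the same list applies to females only, so conditional criteria are normal there. The problem is conditioning on arm.

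**Conclusion.** The point holds as a matter of structure: a stated rule removes people after assignment from one arm only, and no outcomes are planned for them. Its effect is probably small and its direction is unknown. Under the assumed 2-10% failing and 0.5 SD difference, the bias is 0.01-0.05 SD without baseline adjustment, and 0.004-0.02 SD if the difference is stable and baseline drinking is in the model. The highest type I error is about 0.058, in the outcome-only case. A larger difference or a higher failure rate would raise these figures, and the documents do not fix either. Severity is minor to moderate, and it rests on how little the remedy costs, not on evidence of serious bias.

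**What to change.** 1. Keep the safety rule that stops the current, but reword exclusion (8) and the Baseline paragraph so that failure at 1.5 mA ends stimulation and not study participation.
2. Collect Form 90 from these participants at the post-treatment and 2-month time-points. Because those visits are timed from the end of the sessions, set the dates from the scheduled end of the group they would have joined.
3. State in Study Data II that they are included in their assigned arm in the primary analysis, and report tolerance failures by arm.
4. If they are offered MBRP, deliver it so that the lack of stimulation does not reveal their arm to therapists, peers or outcome interviewers. Examples are fitting the device on the sham setting if they tolerate the brief ramp-up, or treating them outside the mixed groups.
5. If the effect in people who tolerate the current is also wanted, give it as a supplementary estimate: the as-randomised effect divided by the tolerating share (for example 0.387 / 0.90 = 0.43). This assumes that assignment has no effect on non-tolerators.

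Testing tolerance in everyone before allocation would remove the asymmetry, but it exposes future sham participants to real current and so puts the blind at risk. It is a trade-off and not part of this recommendation.

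**Cost.** An IRB amendment to protocol and consent wording. With 1-4 people failing, 2-8 extra interviews. At the rates in Participant Compensation this is at most 100 + 40 + 10 + 20 + 50 = USD 220 each, or USD 220-880 in total. It is USD 300-1,200 if they also attend sessions and complete the session questionnaires (USD 80 each). Power falls as shown above at unchanged N. Restoring it is optional: 4-21 more participants at up to USD 400 each, or USD 1,600-8,400 in participant payments, plus group, therapist and EEG time. A possible expectancy loss in the few retained failures should be acknowledged in the report.

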## II. *Participant Enrollment*

Up to 350 individuals who want to reduce their drinking will be recruited for the study.

## III. *Recruitment and Screening Procedures*

Flyers posted in the Albuquerque metropolitan area, postings on online advertising sources (e.g. Craigslist), social media (e.g., Facebook), newspaper and radio advertisements, and flyers posted at treatment agencies and primary care provider offices will be the primary methods of recruitment. We will also recruit participants through referrals from studies of non-treatment seeking heavy drinkers currently being conducted at the Mind Research Network (MRN) and at CASAA (IRB through the HRRC). Study staff on the MRN and CASAA studies will be given recruitment information (e.g., the approved study flyer) to provide the information about our study for treatment seekers who are excluded from their studies of non-treatment seekers. Similar strategies have been used to successfully recruit larger sample sizes in previous studies. Participants will undergo an initial telephone screening to ascertain interest in the research study, interest in reducing drinking, and self-reported right handedness, as well as absence of the exclusion criteria. If they meet the basic requirements of the study, we will then check the public databases (nmcourts.gov) for information about arrests, charges, or convictions of violent crimes. If they are not listed in the nmcourts.gov for violent crimes in the past 2 years or any history of assault with a deadly weapon, then they will be scheduled for an eligibility assessment session, during which time the baseline stimulation session will be conducted, a medical history form and handedness questionnaire will be administered, and informed consent will be obtained. A second check of nmcourts.gov will then occur to confirm that the individual was not arrested, charged, or convicted between the screening session and the baseline assessment. In addition, participants will complete a pregnancy test (for women who could be pregnant) and will be breathalyzed to ensure a BrAC of 0.0. In terms of minority inclusion, individuals of all racial/ethnic backgrounds will be eligible. The racial/ethnic breakdown is expected to reflect the demographics of the Albuquerque area (i.e., predominantly Caucasian/non-Hispanic or Hispanic). Furthermore, we will provide flyers to grassroots minority organizations in the Albuquerque metropolitan area to increase the awareness of our research among minority groups. In addition, we will work on reducing the logistical and psychological barriers to participation among minority groups by providing transportation (bus vouchers), and addressing issues such as fear or distrust of research and the lack of familiarity with research procedures like randomization. In terms of gender composition, we expect that the final sample will be 40% female.

## IV. *Informed Consent Process*

Following phone screen, eligible participants will be invited to the Psychology Clinical Neuroscience Center (PCNC) for the baseline session, which includes being breathalyzed to ensure a breath alcohol concentration (BAC) of 0.0 and the informed consent process. At the first appointment, prior to any testing, consent forms approved by the UNM IRB will be administered by an approved research team member in a confidential office. Research staff will review the consent form, page by page, with each participant and solicit answers to critical questions (such as, "What are the limitations of confidentiality?" and "What are the risks associated with this study?") at the end of each section to ensure that the participant has understood these issues. The consent process will be documented in the participant's file on a dated consent documentation note form. Consent forms will be at the 6th grade reading level. Signed consent forms will be stored separately from participant data in a secure location in the PI's locked office. Participants will be given copies of signed consent forms at this appointment.

We are requesting a waiver of HIPAA Authorization for the disclosure of PHI for the study's use of an eligibility screening form administered over the phone. Since the form is administered without the physical presence of the potential participant, we would be unable to obtain their written authorization to disclose the information asked for on the form. All PHI, aside from the first and last name of the

participant, will be destroyed for participants who are screened out of the study at the time when it is determined that they are not eligible to participate. The first and last names of participants who screen out will be kept to prevent attempts at re-screening into the study. First and last names of those who screen out will be deleted at the end of data collection. All other elements of the research study, aside from any described on other waiver requests, will proceed only if normal HIPAA authorization procedures have been conducted.

For economic and time efficiency reasons, the research could not practicably be conducted without the phone screen. We collect important information during the phone screen that allows us to determine eligibility for research protocols. For participant convenience, it is more practical to gather this information over the phone rather than by scheduling appointments for such brief procedures. This also improves job efficiency for research staff, as they can dedicate their appointment slots to individuals who meet preliminary study inclusion criteria.

We need to control for several variables in the study, and we could not fully evaluate our proposed hypotheses without access to information allowing us to determine specific characteristics. A majority of the information on the phone screening form also determines whether the participant can safely take part in the research and is used to protect individuals (i.e. individuals who may have heart disease or be pregnant). There is no reason to schedule research appointments with individuals who are ineligible for the intervention.

Individuals who are not eligible for the research will be offered a list of community resources for additional alcohol and mental health treatment. The same list will be offered to individuals who are eligible to participate in the research and who want or need additional resources.

